#### **Exploratory Objectives:**

- To evaluate the frequency of subjects with elevated liver function tests (AST, ALT or total bilirubin).
- To evaluate the frequency of subjects with ALT or AST elevations > 3x ULN in temporal association with nausea, vomiting, anorexia, abdominal pain or fatigue.
- To explore the contributions of gender, age and exposure to rimegepant to abnormalities in AST, ALT, or bilirubin.
- To investigate the time on treatment and cumulative exposure associated with: (1) hepatic related SAEs and treatment discontinuations; (2) elevations in ALT or AST > 3x ULN with concurrent elevations in bilirubin > 2x ULN.
- To evaluate the number of headache days and severity of migraine attacks while subjects are treated with rimegepant relative to the observational period.
- To evaluate the effect of rimegepant treatment compared to baseline on the 20-Item Migraine-Specific Quality of Life Questionnaire v 2.1 (MSQoL).
- To evaluate the effect of rimegepant treatment compared to baseline on the Migraine Preference of Medication (PoM).

- To examine the scores on the Sheehan Suicidality Tracking Scale.
- To evaluate the effect of rimegepant treatment compared to baseline on the Satisfaction with Medication survey.
- To evaluate the effect of rimegepant treatment compared to baseline on the Migraine Disability Assessment (MIDAS)
- To evaluate the effect of rimegepant treatment compared to baseline on the Clinical Global Impression change (CGI-c) scale.

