## 8.2.1 Collection and Reporting of Non-Serious Adverse Events

The collection of non-serious AE information should begin at the initiation of study drug. Non-serious AE information should also be collected from the start of a placebo lead-in phase or other observational period intended to establish a baseline status for a patient.

Non-serious adverse events should be followed until conclusion or stabilization, ore reported as SAEs if they become serious. Follow-up is also required for non-serious AEs that cause interruption or discontinuation of study drug or those that are present at the end of study treatment.

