If in the 2-8 or 9-14 moderate to severe migraines/month group, patients will be instructed to take study medication at the onset of a migraine (of mild to severe intensity), with a maximum of one tablet per day. If in the 4-14 moderate to severe migraines/month group, patients will be instructed to take study medication every other calendar day, regardless of whether the patient has a migraine. However, they may take a tablet at the onset of a migraine (of mild to severe intensity), even if the migraine begins on a day they are not scheduled to dose.

Patients are required to record migraine occurrence and severity and all study medication doses in the eDiary and standard of care migraine treatment taken in the paper diary. Patients will also use the eDiary to complete the PoM and SM.

Study visits will be roughly every 2 weeks during the first month and then every 4 weeks until Week 52 (or Week 12 for patients in the EOD+PRN dosing group).

Patients will return to the study site at the end of Week 52 (or Week 12 for patients in the EOD+PRN dosing group) for the End of Treatment (EOT) Visit. There is also a Follow-Up Visit 14 days after the Week 12/Week 52/EOT Visit.

Protocol Version 5.0 was amended to Version 6.0 to re-open study enrollment in the 2-8 moderate to severe migraine attacks per month group to approximately 20 subjects at select sites in order to assess safety of rimegepant in combination with FDA-approved calcitonin gene-related peptide (CGRP) antagonist biologics (Aimovig™, Ajovy™, Emgality™). Patients at select sites with a history of 2-8 moderate to severe migraines/month taking a stable FDA-approved CGRP antagonist biologic will be instructed to take a maximum of one tablet per calendar day for 12 weeks to treat migraines of mild, moderate, or severe intensity. These subjects will follow the same study visit schedule as subjects in the 12-week EOD+PRN dosing group.

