Rates of multiple on-treatment, cumulative and mutually exclusive LFT elevations will be summarized using descriptive statistics for treated subjects (1) enrollment group and overall, and (2) subgroup level and overall for key extrinsic exposure factors. For each subject and LFT elevation endpoint, the rate is defined as total number of elevations/total number of non-missing values during the on-treatment period. Multiple values on the same collection date will be counted only once.

The number and percentage of subjects with time to first on-treatment LFT elevations ($ALT > 3 \times ULN$; $AST > 3 \times ULN$; ALT or $AST > 3 \times ULN$) will be presented by enrollment group and overall for treated subjects with on-treatment LFT elevations in the following categories: ≤ 2 , > 2 to ≤ 4 , > 4 to ≤ 8 , ..., > 48 to ≤ 52 , > 52 weeks. Time to elevation is calculated as $(LFT \text{ collection date} - \text{study drug first dose} + 1)/7$.

In all of these analyses described in this section, subjects must have non-missing LFT data (i.e., ALT , AST , TBL , or ALP) in the safety analysis period to be included.

4.6.3.2 *ALT or AST > 3 x Upper Limit of Normal (ULN) Concurrent with Nausea, Vomiting, Anorexia, Abdominal Pain or Fatigue*

AST or $ALT > 3 \times ULN$ elevations that are concurrent with nausea, vomiting, anorexia, abdominal pain or fatigue will be summarized, as the number and percentage of subjects experiencing this concurrently, in the same table as other LFT elevation endpoints described in Section 4.6.3.1. For a given safety analysis period (pre-treatment, on-treatment, follow-up), an LFT elevation is concurrent with an AE of interest if the imputed AE start date is $+\/- 7$ days inclusive of the LFT collection date; both the LFT collection date and the imputed AE start date must also be in the safety analysis period. Refer to the BHV3000 Core SAP for AE start date imputation. The following will be used to identify the AEs of interest: nausea, vomiting, anorexia, fatigue, and those containing “abdominal pain”.

4.6.3.3 *LFT Elevations by Gender, Age, and Rimegepant Exposure*

See Section 4.6.3.1.

4.6.3.4 *Secondary Safety Endpoints by Rimegepant Exposure*

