- Hepatic-related AEs leading to study drug discontinuation (secondary safety endpoint, see Section 4.6.2).

4.8.3 **Laboratory Tests**

Clinical safety laboratory testing will be performed at early termination and the following visits: Screening; Baseline; Weeks 4, 24, and 52 for the 52-week PRN (2-8) and (9-14) dosing groups; Weeks 4 and 12 for the 12-week EOD+PRN and PRN (2-8) dosing groups. Urinalysis will be collected at early termination and the following visits: Baseline; Week 52 for the 52-week PRN (2-8) and (9-14) dosing groups; Week 12 for the 12-week EOD+PRN and PRN (2-8) dosing groups. Lipids (cholesterol, HDL cholesterol, LDL cholesterol, triglycerides) will be collected at early termination and the following visits: Baseline; Weeks 24 and 52 for the 52-week PRN (2-8) and (9-14) dosing groups; Week 12 for the 12-week EOD+PRN and PRN (2-8) dosing groups. LFTs (ALT, AST, ALP, TBL, direct bilirubin) will be collected routinely at Screening, Baseline, all visits during the treatment period, early termination, and Follow-up Week 2 for all enrollment groups.

Clinically significant laboratory abnormalities will be identified as grade 3 to 4 laboratory test results. Refer to the BHV3000 Core SAP for laboratory tests of clinical interest and toxicity grading. Laboratory test groups of clinical interest will include hematology, serum chemistry, and urinalysis.

LDL cholesterol and triglycerides will be analyzed as separate laboratory test parameters according to 8-hour fasting status: fasting \geq 8 hours; not fasting \geq 8 hours; overall. Refer to the BHV3000 Core SAP for additional details.

Tables, listings, and figures (TLFs) will be provided to show data in both Systeme Internationale (SI) and United States (US) unit systems, if applicable.

Tables will present results by treatment group and overall, and laboratory tests alphabetically within laboratory test group, as applicable. In analyses of the worst abnormality or category in a safety analysis period, subjects must have a non-missing measurement in the safety analysis

period to be included for a given parameter. In shift from baseline analyses, subjects must have a non-missing measurement at baseline and in the safety analysis period to be included for a given parameter.

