5.3 Derived Dates

Derived dates for defining analysis periods are defined as follows:

- OP start date/time: Earliest complete date during the screening epoch in the eDiary.
- OP end date/time: Latest complete date during the screening epoch in the eDiary.
- LTT start date/time: Earliest complete date during the treatment epoch in the eDiary.
- LTT end date/time: Latest complete date during the treatment epoch in the eDiary.
- Study drug first dose date/time: Earliest complete date where subjects indicated that they took medication during the treatment epoch in the eDiary.
- Study drug end dose date/time: Latest complete date where subjects indicated that they took medication during the treatment epoch in the eDiary.
- Study drug last dose date/time: Study drug end dose date derived only for subjects who have non-missing completion status on the Study Exit Status CRF. Thus, in an interim analysis, all post-treatment data will be included for a subject who is still on study. At the last database lock, the last dose date will be equal to the end dose date for treated subjects.
- EOT visit date: Maximum of the following: (1) LTT end date/time; (2) latest complete visit date excluding folder name “follow-up safety visit” on the Visit Date CRF. This is derived only for subjects who have non-missing completion status on the Study Exit Status CRF.

- Last contact date: (1) Complete death date, if it exists; (2) otherwise, the maximum complete date of the following: AE start/stop; ECG; eDiary; enrollment; informed consent; laboratory collection; non-study medication start/stop; physical measurement; procedure; rating scale; questionnaire; screening; study completion/discontinuation; vital sign; visit.

No imputations are performed on these derived dates. Complete dates are those with valid, non-missing day, month, and year.

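### The rule pairing ALT/AST > 3x ULN with symptoms looks only at symptom onset, so a symptom that began more than 7 days before the draw and is still present is not counted

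*SAP*

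**What the plan says.** The exploratory objective in Protocol 2.2, repeated in SAP 1.2.3, is the frequency of subjects with ALT or AST > 3x ULN "in temporal association with nausea, vomiting, anorexia, abdominal pain or fatigue".

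SAP 4.6.3.2 turns this into a date rule: "an LFT elevation is concurrent with an AE of interest if the imputed AE start date is" within plus or minus 7 "days inclusive of the LFT collection date". It adds a second condition: "both the LFT collection date and the imputed AE start date must also be in the safety analysis period". Neither condition refers to the AE stop date or to whether the AE is ongoing. The Core SAP is cited in that section only for imputing start dates, and nothing else in the two documents adds a rule for ongoing symptoms.

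The result is one of the composite rows of the LFT elevation table in SAP 4.6.3.1. That table is produced by enrollment group for each safety analysis period, and on treatment for every subgroup of interest.

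**The concern.** A symptom that is present on the day ALT or AST exceeds 3x ULN is associated in time with that elevation on any ordinary reading of the objective. Under the rule its status depends only on when it began. Nausea that starts 7 days after the draw qualifies. Fatigue that started 8 days before the draw and is present on the day does not. Changing the window width would move this boundary but would not remove it, because the cause is that duration is ignored.

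The symptoms lost are the longer-lasting ones. Protocol 1.3.4 names change in liver function tests as the main AE of interest and asks investigators to watch for liver-related symptoms, so a low count in this row could be read as reassurance that the definition does not support.

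**Working it through.** The plan states no rate, sample size or precision for this endpoint, so there is no figure to reproduce. The check is of the definition.

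**Inputs**
- Window: 7 days either side of the draw, inclusive, which is 7 + 1 + 7 = 15 calendar days of onset (SAP 4.6.3.2).
- Visit spacing: "Study visits will be roughly every 2 weeks during the first month and then every 4 weeks until Week 52" (SAP 2.1).
- Draws: LFTs "will be collected routinely at Screening, Baseline, all visits during the treatment period" (SAP 4.8.3), so scheduled draws are about 28 days apart after Week 4. Protocol Table 1 allows plus or minus 7 days on visits from Week 8.
- Stop dates: collected, since the last contact date uses "the maximum complete date of the following: AE start/stop; ECG; eDiary" (SAP 5.3). Also, "Non-serious adverse events should be followed until conclusion or stabilization" (Protocol 8.2.1).

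**Step 1: test cases.** The elevated draw is on day 0. The present rule is |start − draw| ≤ 7. The amended rule is the present rule, or start ≤ draw ≤ stop.

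| Symptom days | Present at draw? | Present rule | Amended rule |
|---|---|---|---|
| −8 to +5 | yes | no | yes |
| −10 to +3 | yes | no | yes |
| −21 to +10 | yes | no | yes |
| −7 to 0 | yes | yes | yes |
| 0 to +1 | yes | yes | yes |
| +7 to +9 | no | yes | yes |
| −20 to −9 | no | no | no |

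The two rules differ only for symptoms that began more than 7 days earlier and are still present. The amended rule contains the present one, so relative to it the present rule can only give an equal or lower count.

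**Step 2: illustration by assumed duration.** Take a symptom of D days that covers the draw, with onset equally likely on each of days 0 to D − 1 before it. Onsets 0 to 7 days before are captured, which is 8 days, so the share captured is min(1, 8/D):
- D = 10: 8/10 = 80%
- D = 14: 8/14 = 57%
- D = 21: 8/21 = 38%
- D = 28: 8/28 = 29%

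**Step 3: illustration by visit spacing.** Let draws be k days apart, with the symptom starting after the earlier draw and lasting to the later one.
- Only the later draw elevated: k − 8 of k onset days are missed. For k = 28 this is 20/28 = 71%; for k = 14 it is 6/14 = 43%. With the plus or minus 7-day visit windows, k can run from 14 to 42, and 34/42 = 81%.
- Both draws elevated: k − 15 of k onset days are missed, or none if k ≤ 15. For k = 28 this is 13/28 = 46%; for k = 14 it is 0.

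Steps 2 and 3 count possible onset days. They assume no unscheduled draws, and Step 2 assumes the durations. Neither estimates the share of subjects missed.

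**The case against.** The strongest defence is that matching on onset is a deliberate choice in favour of specificity. Nausea and vomiting are features of migraine (Protocol 1.4), and treatment runs for up to 52 weeks. An AE may be followed only to stabilization, so it may never close. Fatigue that began in Week 3 and stayed open would pair with an ALT rise in Week 40 under a rule that counts ongoing symptoms. This stands as a real cost, and it is the reason to keep the onset-only count alongside. It does not justify leaving out a symptom that is known to be present at the draw.

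It can also be said that a worsening may be entered as a new AE with its own start date, since the AE definition in Protocol 8 includes worsening of a pre-existing condition. That could recover some cases, but the two documents do not settle it, and the AE counting rules are in the Core SAP, which was not available.

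The impact is limited. The row is exploratory and descriptive, with no confidence interval planned. One qualifying pair of elevation and symptom is enough for a subject to count. By-subject AE listings (SAP 4.8.2) and LFT listings (SAP 4.8.3) keep the raw data, although they must be joined by hand. The individual LFT plots in SAP 4.6.3.1 mark treated migraine onsets and period starts, not these symptoms.

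A reader might go further and infer that every symptom starting before the draw is lost. That is not so: onsets 0 to 7 days before are counted. A reader might also take the 8/D shares as the understatement of the reported count. The documents give no durations or rates to support that.

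**Conclusion.** The point holds as a modest one. Under SAP 4.6.3.2, a symptom that began more than 7 days before an ALT or AST > 3x ULN draw and is ongoing at it is classed as not concurrent. This is narrower than the stated objective and can understate the count. The direction is certain relative to a rule that also counts ongoing symptoms. The size is unknown, and the percentages above rest on assumed durations or on idealised visit spacing.

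It would be wrong to infer that the trial's main hepatic evidence is compromised. The secondary endpoints in SAP 4.6.2 are same-date ALT or AST with bilirubin, and hepatic-related AEs. None of them uses this rule.

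**What to change.** In SAP 4.6.3.2, count an AE of interest as concurrent with the elevation if either:

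(a) its imputed start date is within 7 days either side of the LFT collection date, as now; or

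(b) its imputed start date is on or before the LFT collection date, and its stop date is on or after that date or the AE is ongoing.

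Keep the present requirement that the AE start and the draw fall in the same safety analysis period. A symptom that starts in one period and is ongoing at a draw in the next will still not be counted, and a footnote should say so.

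State a convention for partial as well as missing stop dates. For example, treat the AE as ongoing unless the known part of the date shows that it ended before the draw. Report the onset-only count (a) as a separate row, so that long-running, non-specific symptoms can be told apart.

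A broader rule, under which the AE interval need only overlap the 7-day window, is not needed. It would also admit symptoms that resolved before the draw, such as one lasting from day −20 to day −5.

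The cost is a short change to the SAP text, one programming condition, one extra table row and the stop-date convention. No new data are collected. The drawback is that some long-standing symptoms unrelated to the elevation will be counted under (b).

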4.6.3.6 Migraine-Specific Quality of Life

Impact of treatment on patient-reported quality of life is assessed using the MSQoL, which is a 14-item questionnaire that has been validated in migraine patients to assess the effects of migraines on their daily activities over the past 4 weeks. The MSQoL will be evaluated at early termination and the following visits: Baseline; Weeks 12, 24, 36 and 52 for the 52-week PRN (2-8) and (9-14) dosing groups; and Week 12 for the 12-week EOD+PRN and PRN (2-8) dosing groups.

The MSQoL consists of the following 3 domains: (1) restrictive role function, (2) preventive role function and (3) emotional function. Values and changes from baseline in transformed scores for each domain will be summarized using descriptive statistics (including two-sided 95% normal CIs for mean change) at baseline, each scheduled visit, and the last post-baseline visit by enrollment group and overall. Refer to the BHV3000 Core SAP for deriving transformed scores for each domain.

4.6.3.7 *Preference of Medication (PoM)*

The PoM is a 5-point rating scale that measures the patient's preference of study medication to previous medications to treat migraine pain. The 5 preference categories are: much better, I prefer this medication; slightly better than the previous medication; about the same as the previous medication; slightly worse than the previous medication; much worse, I prefer my previous medication. The PoM will be evaluated with the eDiary at early termination and the following visits: Weeks 24 and 52 for the 52-week PRN (2-8) and (9-14) dosing groups; Week 12 for the 12-week EOD+PRN and PRN (2-8) dosing groups.

The number and percentage of subjects with PoM data and in each category will be tabulated at each scheduled visit and the last post-baseline visit by enrollment group and overall.

Percentages for categories will be based on subjects with PoM data at each visit, along with two-sided Agresti-Coull 95% CIs for each percentage. Refer to the BHV3000 Core SAP for additional combined categories.

4.6.3.8 *Sheehan-Suicidality Tracking Scale (S-STS)*

The S-STS is a prospective, self-reported rating scale that contains 16 questions to track both treatment-emergent suicidal ideation and behaviors. In the event the subject is unavailable, the S-STS clinician-administered rating scale will be completed that contains 6 yes/no questions. The S-STS will be evaluated at Screening, Baseline, all subsequent visits during the treatment period, and early termination for all enrollment groups.

Refer to the BHV3000 Core SAP for calculating self-reported S-STS ideation subscale, behavior subscale, and total scores.

Values and changes from baseline in the self-reported S-STS ideation subscale, behavior subscale, and total score will be summarized as continuous parameters at baseline and the worst (highest) score in safety analysis periods by treatment group and overall. The table will also present the number and percentage of subjects in the worst (highest) score change from baseline category (i.e., < -1, -1, no change, 1, > 1) in safety analysis periods by treatment group and overall for the ideation subscale, behavior subscale, and total score.

Results will be summarized on-treatment for treated subjects, and follow-up for follow-up subjects. Subjects have a non-missing measurement in the safety analysis period (plus baseline for worst score change) to be included for a given parameter.

4.6.3.9 *Satisfaction with Medication (SM)*

The SM is a 7-point rating scale that captures the subjects' perception of whether they are satisfied with their headache medication. The 7 satisfaction categories are: completely satisfied, could not be better; very satisfied; somewhat satisfied; neither satisfied nor dissatisfied; somewhat dissatisfied; very dissatisfied; completely dissatisfied, could not be worse. The SM will be evaluated with the eDiary at early termination and the following visits: Weeks 24 and 52 for the 52-week PRN (2-8) and (9-14) dosing groups; Week 12 for the 12-week EOD+PRN and PRN (2-8) dosing groups.

The number and percentage of subjects with survey data and in each category will be tabulated at each scheduled visit and the last post-baseline visit by enrollment group and overall. Percentages for categories will be based on subjects with survey data at each visit, along with two-sided Agresti-Coull 95% CIs for each percentage. Refer to the BHV3000 Core SAP for additional combined categories.

4.6.3.10 Migraine Disability Assessment (MIDAS)

The MIDAS is a retrospective, patient-administered, 5-item questionnaire that measures headache-related disability as lost time due to headache from paid work or school, household work and non-work activities. The MIDAS will be evaluated at early termination and the following visits: Baseline; Weeks 12, 24, 36 and 52 for the 52-week PRN (2-8) and (9-14) dosing groups; Week 12 for the 12-week EOD+PRN and PRN (2-8) dosing groups.

Values and changes from baseline in the total, absenteeism, presenteeism, and item scores will be summarized using descriptive statistics (including two-sided 95% normal CIs for mean change) at baseline, each scheduled visit and the last post-baseline visit by enrollment group and overall. Refer to the BHV3000 Core SAP for calculating the total, absenteeism, presenteeism, and item scores.

